7.1.3 Per-protocol Population

The per-protocol (PP) population will consist of all participants in the mITT population who had a duration of treatment exposure of at least 28 days (criteria for replacement) and who do not have a protocol deviation that may impact efficacy with a start date for the deviation before initiation of study treatment.

Note that in the case of participants who have a protocol deviation with a potential impact on efficacy which occurs after initiation of treatment, the participant will remain in the PP population but all data collected after the protocol deviation occurred will be excluded from any analyses performed using the per-protocol population.

Deviations that may affect efficacy are shown in [Table 2](#).

Table 2 Protocol Deviations with a Potential Impact on Efficacy

Description	Evaluation Period	Impact on per-protocol analyses
Not meeting inclusion criteria 3, 4, or 6 or meeting any of exclusion criteria 1-12 or 27	Baseline	Exclude participant from the PP population.
Use of any prohibited medication (Section 5.3.2.3)	Throughout study	If start date of prohibited medication is before date of first dose of study drug then exclude participant from PP population. Otherwise, include participant in PP population but exclude all data collected on or after start date of prohibited medication.
Compliance with study drug <80%	Evaluated in 8-week periods (Weeks 1-8 and 9-16)	If participant is non-compliant within Week 1-8 treatment period, then exclude from PPS. If participant is non-compliant only within the Week 9-16 treatment period then include in the PPS but exclude all data collected after the Week 8 visit date.
>7 consecutive days with no study medication without participant being permanently withdrawn from study medication	Throughout study	Participant will not be excluded from the PP population, but all data collected after the 8 th consecutive day with no study medication will be excluded.
>14 total days with no study medication (does not need to be continuous)	Throughout study	If a participant's dosing log shows >14 days in total with no treatment taken then they will be excluded from the PP population.
Incorrect study treatment taken	Throughout study	Participants will not be excluded from the PP population. If a participant received a study drug other than that received at the start of the study, then exclude all data collected on or after the date at which the treatment change occurred.

Description	Evaluation Period	Impact on per-protocol analyses
Study treatment blind broken	Throughout study	If participant's blind is broken prior to first dose of study drug then exclude from PP population. Otherwise, include participant in PP population but exclude all data collected on or after the date on which the blind was broken.

All analyses using the PP population will group participants according to treatment received at the start of the study.

7.1.4 Safety Population

The safety population will consist of all participants who received any study drug.

All analyses using the safety population will group participants according to actual treatment received. If participants received multiple treatment during the study, they will be assigned to treatment group in the following manner:

- If participant received both active EDP and placebo treatments, they will be assigned to the active treatment group.
- If participant received 2 or more different active dose levels, they will be assigned to the highest dose they received.

7.1.5 Week 16 Responders Population

The Week 16 responders population will consist of all mITT participants who achieved a PASI-50 response at Week 16.

7.1.6 Part B Population

The Part B population will consist of all participants who entered Part B of the study.

7.2 Covariates and Subgroups

If the placebo groups from the 3 cohorts are found to be too heterogeneous to be pooled (see [Section 9.1](#)), the primary and secondary analyses will be performed using within-cohort comparisons of active and placebo treatments, and summary tables will also be produced by cohort.

Subgroups based on baseline severity of disease and obesity will be defined as follows:

- Using baseline PASI score ($<10, \geq 10$)
- Using baseline PGA score (2, 3)
- Using baseline BMI ($<30 \text{ kg/m}^2, \geq 30 \text{ kg/m}^2$)

For the exploratory analysis indirectly comparing the results from this study to those in the UNVEIL study ([Section 9.6.2](#)) the following subgroup of participants will be used:

- Baseline PGA=3 and Baseline BSA 5-10%

For the inferential models defined in [Section 9](#), in addition to the relevant baseline score where applicable, the following covariates will be considered:

- Body mass index (<30 kg/m², ≥30 kg/m²)
- Sex (male, female)
- Country (UK, Poland, Hungary, USA)
- Time since diagnosis (<2 years, ≥2 years)

7.3 Missing Data

Missing efficacy data such as individual item scores will be dealt with as detailed in [Section 5.3.3](#). Otherwise, no imputation of missing efficacy data will be performed, and the use of mixed models will account for missing data.

7.3.1 Partial Dates/Times

Partial dates and times for AEs, medical conditions and concomitant medications will be imputed for the purpose of assigning study phases and calculating duration. Listings will always include the reported date/time information rather than any imputations.

Partial AE onset and concomitant medication start dates will be imputed as follows:

- If only the month and year are specified, and the month and year of the start of treatment are not the same as the month and year of the start date, then use the 1st of the month.
- If only the month and year are specified, and the month and year of the start of treatment are the same as the month and year of the start date, then use the date of start of treatment. If this results in a start date after a known or partial end date, then use the 1st of the month.
- If only the year is specified, and the year of the start of treatment is not the same as the year of the start date, then use January 1 of the year of the start date.
- If only the year is specified, and the year of the start of treatment is the same as the year of the start date, then use the date of the start of treatment. If this results in a start date after a known or partial end date, then use January 1 of the year of the start date.
- If the start date is completely unknown, then use the date of the start of treatment. If this results in a start date after a known or partial end date, do not impute the start date.

Partial AE onset start times will be imputed as follows:

- If the actual or imputed start date is the same as the treatment start date, and the start time is completely missing, then use the time of start of treatment.
- If the actual or imputed start date is not the same as the treatment start date, and the start time is completely missing, then use 00:00.
- If the actual or imputed start date is the same as the treatment start date, and the start time is partially missing (hh:XX) then use the following:

- If the hour is the same as the hour of the start of treatment time then use the complete time of the start of treatment (i.e., both hours and minutes)
- If the hour is not the same as the hour of the start time than use hh:00.
- If the actual or imputed start date is not the same as the treatment start date, and the start time is partially missing (hh:XX) then use hh:00

Partial medical conditions start dates will be imputed as follows:

- If only the month and year are specified, then use the 1st day of the month.
- If only the year is specified, then use January 1st of that year.
- If the start date is completely unknown, do not impute the start date.

Partial AE resolution, medical condition stop dates and concomitant medication stop dates and date last smoked will be imputed as follows:

- If the event, condition or medication is flagged as ongoing, do not impute the stop date
- If only the month and year are specified, then use the last day of the month.
- If only the year is specified, then use December 31 of that year.
- If the stop date is completely unknown, do not impute the stop date.

Partial AE resolution and concomitant medication stop times will be imputed as follows:

- If the actual or imputed stop date is non-missing, and the stop time is completely missing, then use 23:59 on that date.
- If the actual or imputed stop date is non-missing, and the stop time is partially missing, then hh:59 for missing minutes.
- If the actual or imputed stop date is missing, do not impute the stop time.

7.3.2 Adverse Event Information

AEs with missing relationship will be considered 'Related' for summary purposes but recorded as missing in the listings.

7.4 Interim Analyses and Data Monitoring

7.4.1 Purpose of Interim Analyses

The interim analysis will be to aid in the planning of future studies and for a better understanding of the benefit/risk profile of EDP1815.

No decisions regarding study conduct will be made based on the interim results and the study will not be stopped if superior efficacy is found.

7.4.2 Planned Schedule of Interim Analyses

The interim analysis will be performed after the last participant has received their last dose (scheduled for the end of Week 16). All Part A data collected at the time of the data cut will be included in the analysis, so some participants may have data from beyond the Week 16 visit.

7.4.3 Endpoints to be Included in the Interim Analysis

The following endpoints will be included in the interim analysis. Description of the analyses for these endpoints is described in [Sections 8, 9 and 10](#). The list of outputs which will be provided as part of the interim analysis is provided in [Section 15](#).

- Study disposition status
- Treatment disposition status
- Demography
- Baseline disease status
- Exposure to treatment
- Percentage change from baseline in PASI (primary estimand only) main analytical approach (MMRM) and sensitivity analysis (dose response model)
- Change from baseline in PASI - main analytical approach
- Achievement of PASI-50 – main analytical approach
- Achievement of PASI-75, PASI-90 and PASI-100 (summary only)
- Achievement of PGA of 0 or 1 with a ≥ 2 point improvement (summary only)
- Achievement of PGA of 0 (summary only)
- Percentage change from baseline in PGA*BSA (summary only)
- Incidence of adverse events

7.4.4 Adjustment of Confidence Intervals and p-values

As the study will not be stopped if superior efficacy is demonstrated at the interim analysis, there will be no adjustments for alpha-spending.

7.4.5 Practical Measures to Minimise Bias

Outputs featuring unblinded treatment assignments will be created by the unblinded analysis group within [REDACTED] and shared with selective Evelo personnel who are not directly involved in the conduct of the study.

The members of the unblinded team will not be involved in any aspects of study conduct, including in the development of the final summaries and analyses for the study.

Aggregate data from the unblinded results may be more widely shared, including into the public domain, but no data which may have the potential to unblind will be released beyond the unblinded personnel and DMC. Data with the potential to unblind include:

- Efficacy or safety event data where only participants from one treatment group have experienced the event
- Categorical data where one or more categories contains only participants from one treatment group
- Minimum and maximum values for continuous data
- Time to event data where events at single timepoint occurred in only one treatment group

7.4.6 Documentation of Interim Analyses

All unblinded data and summaries, together with any meeting minutes in which unblinded data is discussed will be held in a restricted file structure by the unblinded statistician until after the study has finished and the data has been unblinded after database lock.

7.5 Multi-centre Studies

Results will be presented for all centres combined. For the inferential analyses the effect of country will be assessed for significance in the models.

7.6 Multiple Testing

The statistical analysis for this study will focus on estimation rather than in testing a formal hypothesis. Therefore, no adjustments will be made to control the study-wise type I error rate.

7.7 Visit Windows

All data will be reported according to nominal visits, except for subjects who complete the follow-up Week 20 assessments due to withdrawing from the study before the Week 16 visit. For example, if a Week 2 visit occurred on Day 16 instead of the nominally expected Day 14 it will be reported and included in the summary statistics/statistical analyses for Week 2.

Subjects who withdraw prematurely from the study should complete the assessments required for the follow-up visit (Week 20). However, this data will only be included in tables and figures which are produced **by visit** for subjects who completed the 16-week treatment period and provided Week 16 data prior to the Week 20/follow-up data being collected. Tables and figures which do not show summaries by visit and all listings will include all collected Week 20/follow-up data regardless of whether the subject completed the 16-week treatment period.

Scheduled visits which occur outside the protocol-specified visit window (e.g. if the Week 2 visit occurred on Day 19 outside of the Day 12-18 window), this will be noted as a protocol deviation but data collected will still be included in all summary and analysis tables.

Unscheduled visits will not be included in summary or analysis tables, unless they are baseline measurements or provide data towards a safety endpoint which looks at worst-case post-baseline.

8 Summary of Study Data

All continuous variables will be summarized using the following descriptive statistics: n (non-missing sample size), mean, SD, median, maximum and minimum. The frequency and percentages (based on the non-missing sample size) of observed levels will be reported for all categorical measures.

In general, all data will be listed, sorted by randomized treatment (Placebo, EDP1815), cohort (1, 2, 3), site number and participant number. Relevant listings will include whether the assessment was performed and the date, study day/visit and time of the assessment as applicable.

Unless otherwise specified below, all summary tables will be structured with a column for each treatment. Where appropriate, columns combining all placebo participants, all EDP1815 participants and an overall total column may also be presented.

For summaries of study disposition, demographic and baseline data and study treatment compliance, columns will be ordered and labelled as follows:

- Placebo 1 capsule
- EDP1815 1 capsule
- Placebo 4 capsules
- EDP1815 4 capsules
- Placebo 10 capsules
- EDP1815 10 capsules
- All Placebo
- All EDP1815
- Total

For concomitant medication, efficacy and safety outputs, columns will be ordered and labelled as follows:

- All Placebo
- EDP1815 1 capsule
- EDP1815 4 capsules
- EDP1815 10 capsules
- All EDP1815 (concomitant medication and safety only)

For the efficacy analyses, if the 3 cohorts of placebo participants are found to be too heterogeneous for pooling, selected efficacy tables will also be presented by treatment within cohort, in which case columns will be ordered and labelled as:

- Placebo 1 capsule
- EDP1815 1 capsule
- Placebo 4 capsules
- EDP1815 4 capsules
- Placebo 10 capsules
- EDP1815 10 capsules

For the primary analysis:

- For study disposition summaries where it is appropriate to report information on participants who failed screening, the enrolled population will be used.
- For safety summaries, the safety population will be used.
- For all other summaries and analyses the mITT population will be used, with selected efficacy outputs reproduced using the per-protocol population.

For the final analysis:

- For partial relapse and complete relapse endpoints analysis Week 16 Responders population will be used.
- For duration endpoints and rebound analysis mITT population will be used.
- For or all other summaries and analyses the Part B population will be used.

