4.2.1 Discontinuation From Study Treatment

It may be necessary for a participant to permanently discontinue study treatment. If study drug is definitively discontinued, the participant will be encouraged by the investigator to continue to participate in all scheduled study site visits and assessments, so that study data will be collected for the participant per protocol. Every effort should be made to keep participants in the study.

Dosing may be interrupted at the investigator's discretion due to AE or intercurrent illness for a period of up to 1 week, following which the participant may resume treatment if the investigator considers it safe to do so. The participant should discontinue treatment permanently if the AE occurs a second time.

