4.2.2 Withdrawal From the Study

Participants may withdraw from the study at any time at their own request or they may be withdrawn at any time at the discretion of the investigator for safety, behavioral, compliance, or administrative reasons. The investigator will also withdraw a participant if Evelo terminates the study.

If the participant withdraws consent for disclosure of future information, the sponsor may retain and continue to use any data collected before such a withdrawal of consent.

If a participant withdraws from the study, he/she may request destruction of any samples taken and not tested, and the investigator must document this in the eCRF.

Participants who withdraw from the study during Part A should complete the final assessments listed under the Follow-up Visit (Week 20) at an unscheduled follow-up visit, as detailed in the SoA (Table 6-1). Participants who withdraw from the study during Part B should complete the final assessments at the Early Withdrawal Visit, as detailed in Table 6-2.

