Samples for blood biomarkers		X								X	
BSA involvement (%), PGA, PASI ^{n, o}	X	X	X	X		X		X	X	X	X
LSS, mNAPSI ⁿ		X	X	X		X		X	X	X	X
PSI, DLQI, PA-VAS, SF-36 (vitality and pain), Fatigue ^p		X	X	X		X		X	X	X	X
AE/SAE review	X	X	X	X	X	X	X	X	X	X	X
Concomitant medication review	X	X	X	X	X	X	X	X	X	X	X
Dispense dosing diary		X	X	X	X	X	X	X	X		
Collect/review dosing diary ^q			X	X	X	X	X	X	X	X	

^a Participants who withdraw from the study during Part A should complete the final assessments listed under the Follow-up Visit (Week 20), at an unscheduled follow-up visit. Where relevant and when possible, this should be arranged within 72 hours of the start of a new psoriasis treatment. In the event of early withdrawal from the study, unused study drug is to be collected/collected at this visit.

^b All participants will attend additional follow-up Visits 12 and 13 (see Table 6-2), unless they are considered a 'treatment failure' or meet the criteria for rebound.

^c Recheck inclusion/exclusion criteria at Baseline, before first dose of study drug. Screening laboratory results will be used to confirm eligibility at Baseline/Visit 2 (ie, Day 1).

^d Predose optional genetic samples.

- e BMI will be calculated from the height and weight.
- f Women of child-bearing potential only. Serum HCG at screening, urine thereafter. Pregnancy testing will be performed at the visits indicated or if a menstrual cycle is missed or if pregnancy is otherwise suspected.
- g Participants will fast for at least 8 hours before glucose and lipid blood sampling
- h A single ECG tracing is to be obtained on the day of the visit. If, in the opinion of the investigator, there appear to be clinically significant findings, a second tracing should be obtained during the visit.
- i Blood pressure, pulse, respiratory rate, and temperature are to be checked on the day of the visit.
- j The first dose will be given at the baseline visit, following random assignment to treatment. Subsequent doses are to be taken (away from the study site) once daily in the morning at approximately the same time ± 2 hours. Participants should refrain from consuming acidic drinks 1 hour either side of dosing and from eating 2 hours before dosing and 1 hour after dosing. On days of study site visits during the treatment period (Visit 3 through Visit 10, inclusive), participants may dose at home.

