7.1 Estimands and Intercurrent Events

7.1.1 Primary Efficacy Estimand

The primary estimand will be the effect of EDP1815 on the percent change in PASI score from baseline to Week 16 in the mITT set of all treated participants, regardless of deviations from the protocol. Only data collected while on treatment will be used to account for the intercurrent event of treatment discontinuation (hypothetical strategy based on adherence to treatment only). The posterior mean difference between each active dose and the pooled placebo will be estimated.

Percent change from baseline in PASI score at each visit will be calculated as:

$$100 * (\text{PASI score at Visit} - \text{baseline PASI score}) / \text{baseline PASI score}.$$

A negative percentage change from baseline will indicate an improvement.

For the primary analysis, 3 supportive estimands will also be considered:

- To assess the impact of intercurrent events related to protocol deviations believed to impact efficacy, a supportive analysis will be performed where all data collected after any such identified protocol deviations will be excluded. Participants who had a protocol deviation believed to impact efficacy prior to the first dose of treatment (hypothetical strategy based on adherence to treatment and the aspects of the protocol which impact efficacy) will be completely excluded from this analysis.
- To assess the impact of treatment discontinuation for any reason, a supportive analysis will be performed in which all data collected up to the end of Week 16, including any data collected after treatment discontinuation will be included (treatment policy strategy).
- To assess the impact of treatment discontinuation due to a requirement for alternative therapy, a supportive analysis will be performed where the highest PASI score recorded prior to treatment discontinuation will be applied to all expected visits after treatment discontinuation up to Week 16.

The primary analysis will be performed using a Bayesian MMRM as fully described in Section 7.6.1. Data from visits prior to Week 16 will be included in the model and missing data will not be explicitly imputed.

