7.6.1 Analysis of Primary Efficacy Endpoint

The assumption that the 3 cohorts of placebo participants can be pooled into a single placebo group to be used as a control for all active doses will be examined using mean ($\pm \text{SD}$) plots and box plots of percent change in PASI score against time. In addition, an MMRM will be used to compare the 3 cohorts of placebo participants. The model will include parameters for cohort, visit and baseline PASI score together with cohort*visit and baseline PASI score*visit interactions. Least squares mean (95% CI) estimates for each placebo cohort will be plotted by visit.

A decision will be made by the Evelo study team, based on examination of the above figures and model, on whether the pooling strategy is appropriate.

The primary analysis will be performed using a Bayesian MMRM. The model will include parameters for treatment*visit and baseline PASI score*visit interactions. Body mass index, gender, country, and time since diagnosis will also be considered and included as parameters if found to be significant ($p < 0.05$). The model will not include an intercept. Visit will consist of 6 levels (Weeks 1, 2, 4, 8, 12, and 16) and treatment will consist of 4 levels (pooled placebo, EDP1815 0.8×10^{11} cells, EDP1815 3.2×10^{11} cells, and EDP1815 8.0×10^{11} cells) if the placebo pooling strategy is considered appropriate or 6 levels (Placebo matching EDP1815 0.8×10^{11} cells, Placebo matching EDP1815 3.2×10^{11} cells, Placebo matching EDP1815 8.0×10^{11} cells, EDP1815 0.8×10^{11} cells, EDP1815 3.2×10^{11} cells, and EDP1815 8.0×10^{11} cells) if the placebo pooling strategy is not considered appropriate.

The priors for all parameters in the model will be non-informative and follow a normal distribution with mean 0 and SD 1000. The prior for the variance-covariance matrix will follow an inverted Wishart distribution with degrees of freedom equal to the number of visits and an identity scale matrix. The choice of Wishart distribution is based on it being the conjugate prior of the inverse-covariance matrix of a multivariate-normal random vector.

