9.4.2 Supportive Estimands for the Primary Endpoint

For the primary analysis, three supportive estimands will be considered in order to assess the impact of intercurrent events.

Table 4 Supportive Estimands for the Primary Endpoint

Estimand	Purpose	Population	Intercurrent Event Strategy
Primary Supportive Estimand 1	Assess the impact of protocol deviations which may impact efficacy	PP	Protocol deviation with potential to impact efficacy While on treatment (PASI scores collected after the occurrence of the protocol deviation will be considered missing) Treatment discontinuation for any reason before Week 16 While on treatment (as per Primary estimand)

Estimand	Purpose	Population	Intercurrent Event Strategy
Primary Supportive Estimand 2	Assess the impact of treatment discontinuation for any reason	miITT	
Protocol deviation with potential to impact efficacy
 
Treatment policy (as per Primary estimand)
 
Treatment discontinuation for any reason before Week 16
 
Treatment policy (PASI scores collected more than 4 days after treatment discontinuation will be included). Note that Week 20/follow-up data will still only be included for subjects who completed treatment.

Primary Supportive Estimand 3	Assess the impact of treatment discontinuation due to requirement for alternative therapy	miITT	
Protocol deviation with potential to impact efficacy
 
Treatment policy (as per Primary estimand)
 
Treatment discontinuation due to requirement for alternative therapy before Week 16
 
Composite (highest recorded on-treatment PASI score carried forward to all scheduled visits after treatment discontinuation)
 
Treatment discontinuation for any other reason before Week 16
 
While on treatment (as per Primary estimand)

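### Supportive Estimand 2 (treatment policy) leaves out withdrawal-visit PASI scores dated up to the end of Week 16 that Protocol 7.1.1 includes, and SAP Table 8 does not list the departure (minor; supportive analysis only)

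*SAP*

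**What the plan says.** **Protocol.** Section 7.1.1 defines the treatment-policy supportive analysis as one in which "all data collected up to the end of Week 16, including any data collected after treatment discontinuation will be included (treatment policy strategy" applies. It makes no exception for withdrawal visits. Under Section 4.2.2, participants who withdraw in Part A "should complete the final assessments listed under the Follow-up Visit (Week 20) at an unscheduled follow-up visit". The Table 6-1 row "BSA involvement (%), PGA, PASI" is marked in the follow-up column, so a PASI is taken then. Footnote a of that table asks for the visit within 72 hours of a new psoriasis treatment where relevant and possible, so the score can be dated well before Week 16. Participants who only stop drug are "encouraged by the investigator to continue to participate in all scheduled study site visits and assessments" (Section 4.2.1). In the model of Section 7.6.1, "Visit will consist of 6 levels (Weeks 1, 2, 4, 8, 12, and 16").

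**SAP.** Section 7.7 limits follow-up data in by-visit outputs to data "for subjects who completed the 16-week treatment period and provided Week 16 data prior to the Week 20/follow-up data being collected". It adds: "Unscheduled visits will not be included in summary or analysis tables", with exceptions only for baseline and worst-case safety values. Table 4 says that Supportive Estimand 2 keeps PASI scores taken after discontinuation, then qualifies this: "Note that Week 20/follow-up data will still only be included for subjects who completed treatment". The SAP model (Section 9.4.3) has seven visit levels, Week 20 being the addition. Table 8 lists four changes from the protocol: interim timing, the DLQI sensitivity analyses, the partial-relapse definition and the Part B population.

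**The concern.** A treatment-policy analysis exists to use what was observed after participants stopped drug. For someone who stops and withdraws together, the withdrawal-visit PASI may be the only score taken after stopping. SAP 9.5.6 describes this path for participants who start a new psoriasis treatment: a PASI within 72 hours, then withdrawal. Under the SAP rules that score reaches no visit level of the model. For these participants Supportive Estimand 2 then uses the same records as the primary model, and agreement between the two analyses would partly reflect identical data. A reader who relies on Table 8 would not learn that the analysis differs from the protocol's definition.

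**Working it through.** **1. Text against text.** A PASI taken at withdrawal on, say, Day 50 was collected before the end of Week 16, so Protocol 7.1.1 includes it. SAP 7.7 excludes it twice: the participant did not complete 16 weeks, and the visit was unscheduled. The Table 4 note excludes it again, for Supportive Estimand 2 by name. Keeping it out of the Week 20 level is right. However, Section 7.7 takes these participants out of nominal-visit reporting without assigning their score to any other level.

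**2. How many.** The plan assumes at most 15% discontinue and states 42 active and 21 placebo completers per cohort. This reproduces: 50 × 0.85 = 42.5 and 25 × 0.85 = 21.25, rounded down. Discontinuations at the ceiling are 0.15 × 225 = 33.75 (placebo 0.15 × 75 = 11.25; each dose 0.15 × 50 = 7.5). Affected participants = 33.75 × share who also withdraw × share who attend the visit. The documents give neither share, so both are assumed:

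| Withdraw | Half attend | 80% attend | All attend |
|---|---|---|---|
| 25% | 4 | 7 | 8 |
| 50% | 8 | 14 | 17 |
| 100% | 17 | 27 | 34 |

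If nobody attends, the number is 0.

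**3. Effect on the Week 16 difference.** The design standard error is 25 × √(1/63 + 1/42) = 4.98 points. An illustrative simulation used Week 16 means of -10 (placebo) and -30 (active), SD 25, scores taken 0 to 7 days after stopping, and a six-visit maximum-likelihood MMRM. Everyone who stopped was assumed to withdraw and attend, and nearly every score was placed by moving it to the next open visit. Mean shifts from adding the scores were:

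- about +0.1 points with 15% stopping in both arms;
- -0.2 to -0.4 with placebo 15% and active 7%;
- +0.3 to +0.5 with placebo 7% and active 15%.

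In single trials of the planned size the shift had an SD of 0.7 to 0.8, or 0.6 with half attending.

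**4. What a nearest-visit rule would use.** PASI visits fall on nominal Days 8, 15, 29, 57, 85 and 113, so the midpoints are 11.5, 22, 43, 71 and 99, with ties to the earlier visit. Take withdrawal on each of Days 2 to 116 (115 days), with every earlier visit attended on its nominal day. A score is usable only when the nearest visit has not yet been held:

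| Visit | Usable days | Number | Offsets (days) | Sum |
|---|---|---|---|---|
| Week 1 | 2–8 | 7 | 0–6 | 21 |
| Week 2 | 12–15 | 4 | 0–3 | 6 |
| Week 4 | 23–29 | 7 | 0–6 | 21 |
| Week 8 | 44–57 | 14 | 0–13 | 91 |
| Week 12 | 72–85 | 14 | 0–13 | 91 |
| Week 16 | 100–113 | 14 | 0–13 | 91 |

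In total 60 of 115 days (52%) are usable, with a maximum offset of 13 and a mean of 321/60 = 5.4 days. Moving every score to the next open visit instead would cover 112 days, but with a mean offset of 11.3 and a maximum of 27. It would date 95% of scores forward, put 79% more than 3 days from the assigned nominal day, and let a Day 86 score stand as Week 16.

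**The case against.** The strongest reply is that the protocol does not clearly include the score. Its model has six nominal visits and no rule for placing an unscheduled PASI, and Protocol 7.6 leaves data conventions to the SAP. The SAP also states the restriction openly, inside the definition of the estimand. SAP 5.3.3.1, which mentions only participants who stop drug without withdrawing, suggests it is deliberate. Part of this stands: the protocol includes the score by its wording without saying where it goes, and the reader of Table 4 is told. But a convention for placing data is different from a rule that drops data the estimand includes, and an intended departure still belongs in Table 8.

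On materiality the reply is right. The effect is small, this is one of three supportive estimands, and no formal hypothesis is tested. The simulation is not the SAP model, which is Bayesian with seven visits. Some simulated scores also fall within the 4 days after stopping that SAP Table 3 treats as on treatment. The figures indicate scale only.

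A reader might infer that Supportive Estimand 2 merely repeats the primary analysis. The documents do not support that: participants who stop drug but keep attending still contribute their scheduled scores. Nor is the primary estimand compromised, since Protocol 7.1.1 limits it to on-treatment data.

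**Conclusion.** The discrepancy holds as a minor point about one supportive analysis. The SAP excludes scores that the protocol's wording includes, and Table 8 is silent. Between 0 and about 34 participants are affected at the 15% ceiling. Under the simulation's assumptions the mean shift is within about 0.5 points against a standard error of 4.98. That figure comes from a broader placement than the fix below, whose effect was not simulated separately; the fix would use about half as many scores if withdrawal days were evenly spread.

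A reader might infer a bias in favour of active treatment. The documents give no basis for a direction, and the simulated sign changes with which arm loses more participants. A reader might also reason that 15% of an arm, each 40 points away from what the model implies, would move that arm's mean by 0.15 × 40 = 6 points. That requires one score near the stop to determine the Week 16 value fully, which it does not.

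**What to change.** In SAP 7.7 and Table 4, for Supportive Estimand 2 only:

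- Assign a withdrawal-visit PASI dated up to the end of the Week 16 visit window (Day 116 in Protocol Table 6-1) to the nearest scheduled PASI visit (Weeks 1, 2, 4, 8, 12 or 16) by study day. Use midpoint windows, with ties to the earlier visit.
- Use it only if that visit has no scheduled score. Otherwise list it only.
- Never move it on to the next open visit, and never assign it to Week 20.
- Record the rule in Table 8.

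The cut-off matters little. The SAP elsewhere equates 16 weeks with Day 112; ending there gives 59 of 111 usable days.

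The cost is one rule, one clause and one Table 8 line, with no new data. Some scores will be analysed up to 13 days from their nominal day, and scores close to a completed visit will still go unused. Withdrawal scores within 4 days of stopping would enter this analysis but not the primary, so the contrast between the two would not reflect post-discontinuation data alone. The primary model and all others stay as they are. The 4-day window is itself a SAP addition missing from Table 8; listing it would be documentation only and is separate from this fix.
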